Document Cover page

Official Title of the study: Dietary Patterns, Metabolomics and Colorectal Cancer Risk and Mortality in the Nurses' Health Study and Health Professionals Follow-Up Study

NCT number: not available

Date of the document: originally created on October 1, 2015

History of changes:

C. APPROACH

C1. Aim 1 – K99 phase: To use 3 different approaches to derive 8 dietary patterns and utilize a standardized methodology to compare the best diet for overall health with the best diet for CRC prevention; and further determine if associations with CRC prevention are mediated by biological mechanisms involving inflammation and insulin

Rationale / Preliminary data

We have previously reported that several *a priori* (AHEI, AMED or OMNI) and *a posteriori* (Western or prudent) dietary patterns are associated with overall health (with all-cause mortality as indicator)^{58,59} and with CRC prevention^{12,60} in separate studies. The current proposal goes further to determine the extent to which diets beneficial for overall health are consistent with diets beneficial for CRC prevention. This is important for designing effective dietary guidelines for overall health that are optimized for CRC prevention, given that it is not feasible to have an optimal diet for every disease. We also increase the variety of dietary patterns by including two new patterns – the EDII and CDHR derived using a third and novel approach – the hypothesis-driven approach, that combines the strengths of both *a priori* and *a posteriori* approaches.

Dietary patterns research has overcome the limitations of single nutrient research to a large extent but not completely. Methodological issues have hindered a wider translation of findings from dietary patterns research, the major critique being lack of consistency and scientific rigor in the methods. In Aim 1a we will utilize a standardized methodology to evaluate the associations of the 8 dietary patterns with all-cause mortality as a marker for overall health and with CRC risk, adjusting for the same set of potential confounders, and further investigate in Aim 1b several inflammatory markers (CRP, IL6, TNFR, and adiponectin) and hyperinsulinemia (C-peptide) as mediators of the association between dietary patterns and CRC risk. This will provide an unprecedented opportunity to evaluate the consistency of evidence for the benefits of diet quality for overall health and for CRC prevention, supported by strong epidemiological methods and biological plausibility.

Methodological Approach

Study Population: The NHS was established in 1976 as a prospective cohort of 121,701 U.S. registered female nurses who were aged 30 to 55 years at enrollment.^{61,62} The HPFS was initiated in 1986 as a prospective cohort of 51,529 U.S. male health professionals who were aged 40 to 75 years.⁶³ Blood samples were collected from subpopulations of the NHS (n=32,826) in 1989-1990 and HPFS (n=18,225) from 1993 to 1994, using similar protocols for all cohorts.^{64,65}

Assessment of dietary data: Dietary data are updated every four years in the NHS (since 1980), NHS-II (since 1991) and in the HPFS (since 1986) with a validated semi quantitative food frequency questionnaire (FFQ) assessing habitual intake of foods and beverages over the preceding year. Participants reported how often, on average, they consumed each food of a standard portion size.⁶⁶⁻⁶⁸ We will use average dietary data cumulatively across the multiple FFQs, to reduce within-subject variation and best represent long-term diet.^{69,70}

Assessment of lifestyle factors: We will calculate cumulative body mass index (BMI), physical activity levels, and pack-years smoked.⁷¹ Correlation between technician-measured and self-reported weight was $r=0.96$ in 1980 and 0.97 in 1986 and did not differ by level of BMI.⁷² Our methods that measure physical activity and diet have been rigorously validated in our cohorts.⁷³⁻⁷⁶ We have also routinely collected information regarding a CRC family history in a first-degree relative, post-menopausal hormone therapy, and aspirin use.^{77,78} These long-term lifestyle data at multiple time points provide an unprecedented documentation of individual's lifestyle factors and will allow us to account for within-person variation in the effect of lifestyle on CRC risk.

Assessment of biomarkers: Procedures for the measurement of plasma inflammatory markers (IL6, CRP, TNFaR2, and adiponectin),^{64,79,80} and plasma insulinemic markers (C-peptide, TG, and HDL)^{80,81} have been described. The intra-assay coefficient of variation from blinded quality control (QC) samples ranged from 2.9% to 12.8% for IL6, 1.0% to 9.1% for CRP, 4.0% to 10.0% for TNFaR2, 8.1% to 11.1% for adiponectin, <12% for C-peptide and <1.8% for TG and HDL across batches. In the nested case-control studies in which these biomarkers were measured, samples from cases and their matched controls were analyzed in the same batch. QC samples were randomly interspersed among the case-control samples, and laboratory personnel were blinded to QC and case-control status for all assays. Our group has previously documented the stability of biomarkers in whole blood for 24 to 48 hours.⁸² Participants who provided blood samples were cancer free and similar to their overall cohort with respect to BMI, parity, age at menarche, and past oral contraceptive use.⁸⁰

Ascertainment of CRC incidence^{83,97,98} and mortality:^{80,81} Information on incident cancer and other disease

outcomes have been collected through participants, next-of-kin, or death certification. For any report of CRC, we seek written permission from study participants or next-of-kin to review their medical records. Study physicians review these records and successfully confirm 97% of reported CRC. The National Death Index is used to ascertain deaths and any diagnosis of CRC that contributed to death or was a secondary diagnosis. **Dietary patterns definitions:** We will use 3 different approaches to define 8 dietary patterns: 4 *a priori* patterns (AHEI-2010, DASH, AMED, OMNI); 2 *a posteriori* patterns (Western and prudent); and 2 hypotheses-driven patterns (EDII, CDHR). **1. AHEI-2010:** The 11 components of the AHEI-2010 include vegetables, fruits, whole grains, sugar-sweetened beverages and fruit juice, nuts and legumes, red/processed meat, trans fat, long chain (ω -3) fats, polyunsaturated fatty acids, sodium and alcohol. We will award points for intake of each dietary component on a scale from 0-10, with 10 indicating adherence, 0 no adherence and intermediate scores categorized proportionately.¹³ **2. DASH:**^{84,85} Several different DASH scores exist,⁶ and we will use the one developed (DASH-Fung)⁸⁶ and applied by my mentors,⁶⁰ which is most commonly found in the literature with US populations. DASH-Fung scores 8 components (7 food groups and 1 nutrient)—each worth 5 points—for a total of 40 points.⁸⁶ **3. AMED:** we will use the AMED score that our group adapted for use in a US population.^{59,87} The score rewards 1 point if intake is above the cohort-specific median for vegetables, legumes, fruit, nuts, whole-grain cereals, fish, and MUFAs:SFA and 1 point for intake below the cohort-specific median for red and processed meats. In addition, alcohol intake of 5 to 10 g/d for women and 10 to 15 g/d for men received 1 point. The total score ranges between 0 and 9.^{87,88} **4. OMNI:** the OMNI diet is an improved DASH diet with partial substitution of carbohydrates with protein, about half from plant sources, or with unsaturated fat, predominantly monounsaturated fat.^{89,90} **5. Western pattern and 6. Prudent pattern:** we will derive these two *a posteriori* patterns using principal components analysis.⁹¹⁻⁹³ The factors will be rotated by an orthogonal transformation to achieve a simpler structure with greater interpretability, and the number of factors to retain will be determined using the diagram of eigenvalues.⁹¹ The factor score for each pattern will be calculated by summing intakes of food groups weighted by their factor loadings. **7. EDII and 8. CDHR:** I developed and validated these two patterns (described below) as part of my postdoctoral fellowship work. The manuscripts have been submitted.

Preliminary study 1 - Development and validation of an empirical index of dietary inflammatory potential (EDII): The goal for developing the **EDII** was to empirically create a score based on food groups to assess the overall inflammatory potential of whole diets. We first calculated average daily intakes (per 1000kcal) of 39 previously

defined food groups⁷⁰ from the 1986 and 1990 FFQs in the NHS. We then applied reduced rank regression (RRR) to derive a dietary pattern predictive of three inflammatory biomarkers: CRP, TNFaR2 and IL6. RRR identifies linear functions of predictors (e.g., food groups) that simultaneously explain as much variation in the responses of interest (e.g., biomarkers) as possible. The first factor obtained by RRR was retained for subsequent analyses; (we called this the RRR dietary pattern). We then used stepwise linear regression analyses to identify the most important component food groups contributing to the RRR dietary pattern with the biomarker response score (RRR dietary pattern) as the dependent variable,

[figure not shown]
Table 2: Multivariable-adjusted relative concentrations (95% confidence intervals) of inflammatory markers across quintiles of the EDII in the NHS-II and HPFS							
Quintile 1	Quintile 3	Quintile 5	Ptrend ^a	Quintile 1	Quintile 3	Quintile 5	Ptrend ^a
Nurses' Health Study-II (n=1,002); 1995-1999				Health Professionals Follow-up Study (n=2,633); 1990-1994			
IL6 ^b							
reference	0.99 (0.86, 1.13)	1.13 (0.99, 1.30)	0.09	reference	1.04 (0.96, 1.16)	1.15 (1.05, 1.25)	<0.0001
CRP ^b							
reference	1.25 (0.97, 1.60)	1.41 (1.11, 1.84)	0.08	reference	1.23 (1.09, 1.39)	1.39 (1.21, 1.57)	<0.0001
TNF α R2 ^b							
reference	1.00 (1.01, 1.10)	1.07 (1.03, 1.12)	0.04	reference	1.05 (1.02, 1.09)	1.09 (1.06, 1.13)	<0.0001
Adiponectin ^b							
reference	1.01 (0.92, 1.10)	0.88 (0.81, 0.97)	0.008	reference	0.95 (0.90, 1.00)	0.87 (0.82, 0.92)	<0.0001
Overall inflammatory marker score ^{c,d}							
reference	1.45 (0.89, 2.37)	2.69 (1.64, 4.41)	0.002	reference	1.61 (1.26, 2.07)	2.64 (2.05, 3.39)	<0.0001

^athe p-value for trend is the p-value of the EDII as a continuous variable adjusted for all covariates listed in Footnote #3. ^bvalues are ratio relative concentrations, comparing highest EDII quintiles to the lowest quintile (e.g., Q5/Q1), and back transformed (e^t) since biomarker data were log transformed using natural logarithms prior to analysis; ^{c,d}fully adjusted model were adjusted for age, physical activity, smoking status, batch effects for biomarker measurements, regular aspirin/NSAID use and an inflammation-related chronic disease comorbidity score, and in NHS-II, additionally adjusted for menopausal status and postmenopausal hormone use. Chronic diseases/conditions included in the score were hypertension, cancer, diabetes, high blood pressure, heart disease, and rheumatoid/other arthritis; ^dthe overall inflammatory score was computed by summing z-scores of all four biomarkers for each participant

the 39 food groups as independent variables, and a significance level of $p=0.05$ for entry into, and retention in the model. Intakes of the food groups identified in the stepwise linear regression analyses were weighted by the beta coefficients derived from the final stepwise regression model and then algebraically summed to constitute the EDII score. Higher (more positive) scores indicate more pro-inflammatory diets while lower (more negative) scores indicate anti-inflammatory diets. The EDII is comprised of 18 food groups; 9 are anti-inflammatory and 9 pro-inflammatory. In two independent samples, the NHS-II and HPFS, the EDII significantly

predicted concentrations of several biomarkers (IL6, CRP, TNF α R2, adiponectin and an overall inflammatory marker score as construct validators) (**Table 2**).

Preliminary study 2 - Development and validation of three indices of dietary insulinemic potential: We developed the three indices based on food groups, to assess the insulinemic potential of whole diets: 1) the empirical dietary index for hyperinsulinemia (EDIH), 2) the empirical dietary index for insulin resistance (EDIR) and 3) the composite dietary index for hyperinsulinemia and insulin resistance (CDHR). We used dietary and biomarker data (C-peptide, TG and HDL) in the NHS to develop the three indices, by fitting 2 separate stepwise linear regression models to identify the most important component food groups contributing to hyperinsulinemia (with C-peptide as the dependent variable) and to insulin resistance (ratio of TG/HDL as the dependent variable), the 39 food groups as independent variables, and a significance level of $p=0.1$ for entry into, and retention in the model. Intakes of the food groups identified in the stepwise linear regression analyses were weighted by the beta coefficients derived from the final stepwise

regression model and then algebraically summed to constitute the scores. To create the composite score, we algebraically summed up the different components of both the EDIH and the EDIR to constitute the CDHR. Higher scores on all 3 indices indicate more highly insulinemic diets (hyperinsulinemia or insulin resistance) while lower scores indicate low insulinemic or insulin sensitive diets. The EDHR comprises 24 food groups; 12 are anti-insulinemic and 12 pro-insulinemic. In the HPFS, the EDII significantly predicted concentrations of the overall insulinemic marker score (combination of C-peptide and TG/HDL) as the construct validator (**Figure 1**) and of C-peptide and TG/HDL in separate models.

Statistical Analysis: The primary analysis for **Aim 1a** will prospectively assess associations between each of the 8 dietary patterns and all-cause mortality, and with incident CRC, using Cox proportional hazards regression, with separate models for men and women and in pooled analyses. For CRC, we will investigate associations by anatomic subsite (proximal colon, distal colon, rectum). After >30 years of follow-up, we have confirmed 31,286 all-cause deaths in the NHS and 12,555 in the HPFS.⁹⁴ Also, we have identified 1,764 CRC cases (823 proximal, 521 distal, and 379 rectal cancers) in NHS, and in the HPFS, we documented 1,640 CRC cases (640 proximal, 574 distal, and 426 rectal cancers).⁹⁵⁻⁹⁷ Person-time (in months) for each participant will be calculated from the date of return of the baseline questionnaire in 1980 for women and 1986 for men, until the date of death from any cause or until CRC diagnosis, or June 1, 2012 whichever came first. Cumulatively updated average dietary pattern scores will be calculated using information from all available FFQs up to the 2-year interval prior to the follow-up cycle in which death or CRC diagnosis was confirmed. We will categorize the dietary patterns into quintiles and use the lowest quintile as reference, stratifying the Cox models on calendar year, age in months, to estimate hazard ratios (HR) and 95% confidence intervals (CI) to determine risk of dying from any cause and risk of developing CRC in higher quintiles of dietary patterns. Test for trend will be performed by modeling the dietary pattern scores as continuous variable and deriving the p-value for trend from the Wald test. In multivariable analyses, we will adjust for: BMI, physical activity, age, energy intake, race/ethnicity, educational status, smoking status, family history of CRC, NSAIDs use and additionally for menopausal status and postmenopausal hormone use in women. We will assess effect modification by BMI and physical activity, and incorporate 2-6 year time lags to reduce the potential for reverse causation. Based on the magnitude of risk explained, we will select the best diet in each of the three approaches (*a priori*, *a posteriori* and hypothesis-driven) and conduct a comparative analysis to derive the overall best diet for a healthful lifestyle that maximizes CRC prevention.

Aim 1b will be investigated using dietary and biomarker data from the two cohorts in a cross-sectional study. The 8 dietary patterns will be the main exposures while CRC diagnosis will be the outcome of interest. We will calculate dietary patterns from the 2 FFQs closest to the period of blood draw. That is, the 1986 and 1990

FFQs for the NHS, and the 1990 and 1994 FFQs for HPFS, averaging data across the 2 FFQs. We will then conduct mediation analyses, with the main objective of identifying the direct and indirect effects of each dietary pattern on CRC development, i.e., the effect of the dietary pattern that acts through the proposed mediators (CRP, TNF α R2, IL6, adiponectin, C-peptide) (indirect effect) and the effects that are unexplained by these same mediators (direct effects). The traditional approach to mediation analysis is based on adjusting for the mediator in standard regression models to estimate the direct effect, however, this approach may lead to flawed conclusions.⁹⁸ We will therefore use the regression-based approach described by VanderWeele and Vansteelandt⁹⁹ to estimate the direct and indirect effects of each potential mediator one at a time and cumulative effect for multiple mediators. This approach consists of fitting one model for the mediator, and another for the outcome. The approach has the advantage of assessing several mediators in the same model which would efficiently assess the potential interrelatedness of these mediators. We will use the SAS macro developed by the same authors⁹⁹ to implement the mediation analysis. All statistical tests will be two sided, and we will consider 95% confidence intervals not including one as statistically significant.

Expected outcomes for Aim 1 and impact on the field: To our knowledge, an evaluation of the consistency of evidence for the benefits of diet quality for overall health and for CRC prevention, based on a standardized methodology and plausible biological mechanisms has not previously been conducted. With the completion of this study, we anticipate an increased ability to widely translate findings from dietary patterns research and to design guidelines for healthful lifestyles that are optimized for CRC prevention.

C2. Aim 2 – R00 phase: To identify the set of metabolites predicted by both inflammatory diets and by circulating inflammatory markers and then evaluate the association of this unique inflammatory metabolome with CRC risk.

Aim 3 – R00 phase: To identify the set of metabolites predicted by both insulinemic diets and by circulating insulin markers and then evaluate the association of the unique insulinemic metabolome with CRC risk.

Rationale

Metabolomics, being the sum of the total metabolic processes in a cell, and situated downstream to all the other “omics,”^{49,100} is uniquely suited to assess metabolic responses to dietary stimuli. Few studies have integrated metabolomics data in nutritional epidemiology and have determined the metabolic phenotype of behavioral/psychological dietary preferences.^{49,50} The observed metabolic “fingerprint” or metabolome provides evidence for a link between specific dietary patterns and metabolic phenotypes. Additionally, no prior study has integrated dietary patterns with biomarker and metabolomics data to determine the metabolic phenotype of dietary behavior corroborated by relevant biomarkers. Integrating dietary, biomarker and metabolomics data provides an opportunity to derive unique metabolomes that may help to clearly differentiate between CRC cases and non-cases within the context of CRC early detection or diagnosis.

Methodological Approach

Assessment of metabolite data: plasma metabolites were measured as peak areas by a targeted LC-MS metabolomics platform directed by [name] at the Broad Institute of the Massachusetts Institute of Technology and Harvard University (Cambridge, MA). Metabolite profiling methods were developed using reference standards of metabolites to determine chromatographic retention times, MS multiple reaction monitoring transitions, declustering potentials and collision energies.¹⁰¹ In prior pilot work,¹⁰² our group quantified 257 metabolites from archived plasma to evaluate metabolite interassay reproducibility, reproducibility with delayed processing, and within-person reproducibility over time. Interassay reproducibility was assessed with CVs from 60 duplicate plasma samples donated by participants in the NHS and HPFS, and 20 QC pool plasma replicates. CVs were <20% for 92% of metabolites and generally were similar by plasma anticoagulant type (heparin or EDTA) and fasting time. Metabolite reproducibility over a 24- to 48-h processing delay (n=48 samples) and within-person reproducibility over 1–2 years (n=80 samples) were assessed using

Spearman and intraclass correlation coefficients (ICCs). Approximately 75% of metabolites were reproducible over delays in processing of blood samples (Spearman or $ICC \geq 0.75$, comparing immediate and 24-h delayed processing). Carbohydrates and purine/pyrimidine derivatives were most adversely affected by the processing delay; and 90% of metabolites were reproducible over 1–2 years within individuals (Spearman or $ICC \geq 0.4$).¹⁰² 174 metabolites passed these QC criteria and will be included in the analysis for Aims 2 and 3. We have used this platform in a nested case-control study of pancreatic cancer, with the novel finding that the 3 branched chain amino acids (isoleucine, leucine and valine) were associated with a higher risk of pancreatic cancer (RR, top vs. bottom quintile of sum of 3 amino acids=2.13; 95%CI=1.43-3.15), independent of other risk factors.¹⁰³

Derivation of metabolomic fingerprint scores and statistical analysis: (*metabolomic fingerprint is used interchangeably with metabolomic signature, profile, or pattern*). **Table 3** lists the sample sizes for participants with biomarker (CRP, TNF α R2, IL6, adiponectin, and C-peptide) data from several matched case-control studies, nested within the NHS and HPFS. Participants were matched on cohort, sex, year of birth, smoking status (never, former, current), and fasting status (<8 hours, ≥ 8 hours). In addition to the two dietary pattern scores (EDII and CDHR), we will create two different overall biomarker scores for each participant as follows:

$$\text{Overall inflammatory marker score (infMS)} = z\text{-score}(\log IL6) + z\text{-score}(\log CRP) + z\text{-score}(\log TNF\alpha R2) - z\text{-score}(\log Adiponectin);$$

$$\text{Overall insulinemic marker score (insMS)} = z\text{-score}(\log C\text{-peptide}) + z\text{-score}(\log TG/\log HDL).$$

[figure not shown]
Prior to analysis, concentrations of all metabolites will be log transformed and values normalized to have

mean: 0, standard deviation: ± 1 . The two dietary pattern scores (EDII and CDHR) and the two overall biomarker scores (infMS and insMS) will be trichotomized into tertiles. All data will then be merged and participants randomized to either the training dataset or the validation dataset in a 2 to 1 manner. We will use the training dataset to develop the metabolomic fingerprint scores, and then assess their validity in the validation dataset. We will construct four separate multivariable-adjusted Full Canonical Discriminant Analysis models, to create the metabolomic fingerprint scores, with all 174 metabolites as dependent variables

and the highest and lowest tertiles of the dietary pattern scores and two overall biomarker scores as independent variables (one in each of the four models). To maximize the degree of discrimination, we will exclude participants in the middle tertiles. The canonical coefficients from the principal components' eigenvector encapsulate the greatest degree of discrimination. As such, all 174 metabolites contribute to the computation of the Full Canonical Variable. The metabolomic fingerprint score will include the 20 metabolites with the largest canonical discriminant coefficients (10 largest negative and 10 largest positive), identified by the full canonical discriminant analysis. Ten was determined as the cutoff for inclusion in the metabolomic fingerprint score as we deemed that the identification of 20 (potentially related) metabolites would be sufficient for biological interpretation of the results. The multivariable-adjusted models will include case/control status, cohort, quintiles of caloric intake, smoking status, and age at blood collection. We will not adjust for BMI or

physical activity because we showed in **preliminary studies 1 and 2** that these variables played a more mediating or modification role than a confounding role in the association between inflammatory and insulinemic dietary patterns and respective biomarkers (*[name] et al, submitted*). We will therefore assess effect modification by BMI and physical activity.

To evaluate the performance of the discriminatory variables (i.e., the 4 metabolomic fingerprint scores), we will compute them in the validation dataset, and then conduct four separate un-adjusted and multivariable-adjusted ANCOVAs for each discriminatory variable, with tertiles of each of EDII, CDHR, infMS and insMS as the

Equation 1. Computation of the Metabolite Fingerprint Score

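### Aim 1a keeps averaging in diet reported after an intermediate chronic-disease diagnosis and states no baseline disease exclusion, so disease-driven diet change can bias the mortality hazard ratios; the planned 2-6 year lags remove only part of this

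*Combined protocol and SAP*

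**What the plan says.** The Statistical Analysis paragraph of section C1 defines the Aim 1a exposure as a cumulatively updated average "using information from all available FFQs up to the 2-year interval prior to the follow-up cycle in which death or CRC diagnosis was confirmed". Death and CRC are the only events that end the updating.

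Person-time "will be calculated from the date of return of the baseline questionnaire in 1980 for women and 1986 for men" and runs to death, CRC diagnosis or "June 1, 2012 whichever came first". That is up to 32 years in women and 26 in men. No exclusion for prevalent disease is stated for the mortality analysis. The word incident implies that prevalent CRC is removed for the CRC outcome. The one disease-free statement, "Participants who provided blood samples were cancer free", stands under Assessment of biomarkers and describes blood donors.

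The Aim 1a covariates are BMI, physical activity, age, energy, race/ethnicity, education, smoking, family history of CRC and NSAID use, plus menopausal status and hormone use in women. None is a comorbidity term. Preliminary study 1 did adjust for a comorbidity score: "Chronic diseases/conditions included in the score were hypertension, cancer, diabetes, high blood pressure, heart disease, and rheumatoid/other arthritis".

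The named protection is to "incorporate 2-6 year time lags to reduce the potential for reverse causation". The Limitations section covers follow-up, screening, misclassification and confounding, but not diet change after a diagnosis.

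**The concern.** A diagnosis of diabetes, heart disease, stroke or another cancer raises the risk of death and may lead a person to eat differently. Under the stated rule, diet reported after such a diagnosis enters the average used to explain the later death. The score then partly reflects the illness.

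People already ill in 1980 or 1986 raise the same problem from the first questionnaire, because all their reported diet follows the diagnosis.

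This matters because all-cause mortality is the plan's marker of overall health, and the best diet within each approach is chosen by the size of the association. A bias of several percent in an HR therefore acts on the quantity used for the choice, even when statistical significance is not in doubt.

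**Working it through.** **1. The plan's own figure.** Table 3 gives a minimum detectable association of 1.04 for 43,841 deaths (31,286 + 12,555) at 80% power. For top versus bottom quintile (two fifths of deaths, equal split, two-sided 0.05): exp[(1.960 + 0.842)/√(43,841 × 0.4 × 0.25)] = exp(2.802/66.21) = 1.043. A linear trend over five quintiles gives 1.039. Both round to 1.04, so the figure reproduces.

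On the same basis the standard error of the log HR is 1/66.21 = 0.0151, and the 95% half-width is 1.96 × 0.0151 = 0.030.

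**2. What a lag can remove.** Food frequency questionnaires (FFQs) come every four years (Assessment of dietary data). For a diagnosis 12 years before death:
- 2-year lag: (12 − 2)/4 = 2.5, so two or three post-diagnosis questionnaires stay in the average.
- 6-year lag: (12 − 6)/4 = 1.5, so one or two stay.

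**3. Simulation A (all inputs assumed).** 60,000 people × 6 seeds, 15 two-year cycles, four-yearly questionnaires with within-person SD 0.7, about 8% prevalent disease plus later incident disease, and a Poisson model with age and age squared. Entries are quintile 5 versus 1 mortality HRs, with standard error about 0.007. Percentages are relative to the no-shift HR.

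| Disease mortality HR | Shift toward healthy | No shift | 2-year lag | 6-year lag | Stop + exclude |
|---|---|---|---|---|---|
| 2.0 | 0.2 SD | 0.800 | 0.831 (+3.9%) | 0.827 (+3.4%) | 0.804 |
| 2.0 | 0.4 SD | 0.800 | 0.864 (+8.0%) | 0.854 (+6.8%) | 0.804 |
| 2.5 | 0.2 SD | 0.795 | 0.834 (+4.9%) | 0.829 (+4.3%) | 0.797 |
| 2.5 | 0.4 SD | 0.795 | 0.876 (+10.2%) | 0.863 (+8.6%) | 0.797 |

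Example: 0.827/0.800 = 1.034. On the log scale the range is ln 1.034 = 0.033 to ln 1.102 = 0.097, against the half-width of 0.030 in step 1.

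**4. Simulation B, built separately (all inputs assumed).** 400,000 people, 16 two-year cycles, Mantel-Haenszel rate ratio stratified by age and cycle, true HR 0.80, disease mortality HR 2. The no-shift value is 0.790.

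| Shift | Plan as written | 6-year lag | Stop + exclude |
|---|---|---|---|
| +0.2 SD | 0.826 (+4.6%) | 0.820 (+3.8%) | 0.796 |
| +0.3 SD | 0.845 (+7.0%) | 0.835 (+5.7%) | 0.796 |
| +0.5 SD | 0.886 (+12.2%) | 0.866 (+9.6%) | 0.796 |
| −0.3 SD | 0.735 (−7.0%) | 0.748 | 0.796 |

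- Share of log bias removed by the 6-year lag at +0.2 SD: 1 − ln(0.820/0.790)/ln(0.826/0.790) = 16%. At +0.5 SD it is 20%. About 71% of decedents with a diagnosis had it more than 6 years before death.
- At +0.3 SD, stopping updates alone gives 0.827 and exclusion alone gives 0.827. Both together give 0.796.
- With a true HR of 1.0 and +0.3 SD, the plan as written gives 1.074 and the 6-year lag gives 1.058.

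The Monte Carlo standard error of the log HR in B is about 0.01.

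**The case against.** **What stands**
- The documents report no diet change after diagnosis, so neither the direction nor the size of the bias can be read from them.
- Both simulations adjust for age and omit BMI, activity, smoking, energy and NSAID use, some of which may track illness. The residual bias under the full model is unknown.
- In simulation B the share dying is the same 30.3% at every shift with disease HR 2, so the shift itself does not affect mortality there. That favours freezing the score. If a better diet after diagnosis does lower mortality, freezing discards real exposure.
- Cumulative averaging is a deliberate, referenced choice to represent long-term diet, and the plan says the lags reduce reverse causation, not that they remove it.
- The 1.04 in Table 3 is a departure from 1.00. An HR of 0.83-0.88 with 43,841 deaths would still be easily detected, so the issue is magnitude and not power.

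**Stronger readings the documents do not support**
- *Prevalent disease is included.* The text is silent. It supports only that no exclusion is stated.
- *Dietary patterns are re-ranked, or mortality is biased much more than CRC.* The simulations have one score and one outcome, and similar attenuation of all patterns could leave their order unchanged.
- *Tying the questionnaire cut-off to the cycle of confirmation lets post-diagnosis diet into the CRC models.* The National Death Index sentence ("The National Death Index is used to ascertain deaths and any diagnosis of CRC that contributed to death or was a secondary diagnosis") may suggest late confirmation. However, person-time ends at death or CRC diagnosis, so later diet has no risk time to attach to, and the dead return no questionnaires.

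None of this supplies a stopping rule, a baseline exclusion or a comorbidity term for Aim 1a.

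**Conclusion.** The point holds as a conditional bias in the Aim 1a mortality analysis. The rule is written out, and following it lets diet reported after an intermediate diagnosis into the exposure. The lags help but leave most of the effect in the simulated settings.

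With a true HR of about 0.80, disease mortality HR 2.0-2.5 and a 0.2-0.4 SD shift toward healthy, the distortion is about 4-10% with a 2-year lag and 3-9% with a 6-year lag. Over that range it exceeds the approximate 95% half-width of the log HR.

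A reader might conclude that the bias always runs toward the null. It does so only if the true association is protective and diet improves after diagnosis. A 0.3 SD worsening moves the HR to 0.735, and a true HR of 1.0 becomes about 1.07, both away from the null. Disease frequency, diet shift and disease mortality HR are all assumptions.

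**What to change.** For the Aim 1a mortality analysis, state in the plan:

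- (a) Participants reporting cancer, heart disease, stroke or diabetes at the 1980/1986 baseline are excluded.
- (b) Updating of the dietary score stops at first report of any of these. The pre-diagnosis average is carried forward, and the later person-time and deaths are kept.
- (c) The continuously updated score with the 2-6 year lags is reported as a sensitivity analysis.

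Both (a) and (b) are needed, since either alone left the HR at 0.827 in simulation B. A comorbidity covariate is not an equivalent remedy, because disease may lie on the path from diet to death. Aim 1 promises one standardized method, so the plan should also say whether the same rule applies to the CRC models.

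Cost: some text and modest programming. The ascertainment section says that reports of cancer and other diseases are collected. That baseline and stroke reports are usable in both cohorts is an assumption to confirm. Some deaths are lost to the exclusion (about 11% in simulation A), real diet change after diagnosis is ignored, and the results apply to people free of these diseases at baseline.
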